Study Protocol

Official Title: Optimizing Care for Patients with Dementia: A Comparison of Two Non-Pharmacological Treatment Approaches

ClinicalTrials.gov ID (NCT number): NCT03442322

Protocol Date: December 2017, revised August 2021 due to COVID-19 pandemic

Scientific Background

More than half of the 1.4 million long-term care nursing home (NH) residents have a diagnosis of Alzheimer's Disease and Related Dementias (ADRD), which we will refer to as dementia throughout this report.¹ Residents living with dementia experience devastating negative effects associated with these progressive, irreversible conditions that result in loss of independence and subsequent long-term institutionalization. As the disease progresses, disruptions in the resident's daily routine, difficulty communicating personal needs, and environmental overstimulation or sensory deprivation often trigger the behavioral and psychological symptoms of dementia (e.g., agitation).²⁻⁴ If untreated, these symptoms result in negative side effects such as self-inflicted pain, limited food/liquid intake, accidental falls, and injuries to self or others (e.g., residents, NH staff), increasing the risk of hospitalization and death.⁴

In the early 2010s, more than 30% of NH residents were taking antipsychotic medication.⁵ To reduce this antipsychotic medication use in NH residents, the Centers for Medicare & Medicaid Services (CMS) championed a national initiative to enhance NH dementia care, starting in 2012. This comprehensive program, which had a goal of reducing national NH resident antipsychotic medication use, included NH staff and state surveyor training, established minimum standards for dementia care, and introduced a new quality measure (i.e., the percent of long-stay residents who received an antipsychotic medication) that all CMS certified NHs were mandated to report.⁶

Off-label antipsychotic medications, while commonly used to address the behavioral and psychological symptoms of dementia, have been shown to be ineffective and cause harm to the person living with dementia,⁷ including an elevated risk of death.⁸ By 2019, approximately 23% of NH residents living with dementia were administered off-label antipsychotics.^{5,9} However, these off-label medications have significant negative impacts on the resident's mortality and quality of life, primarily due to inducing withdrawal and lethargy.¹⁰⁻¹²

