The initial study protocol was designed and initiated prior to the emergence of the COVID-19 pandemic. However, with the emergence of the COVID-19 pandemic, our study was modified to also include looking at the impact of the pandemic. Thus, two questions were addressed by this study: (a) is there a statistically significant difference in resident outcomes among NH residents living with dementia based on the non-pharmacological approach to dementia care? And (b) How did these non-pharmacological approaches compare after the emergence of COVID-19 when residents and staff faced social isolation, infection control policies, and staffing shortages? These questions were addressed via three aims:

Aim 1: Compare the effectiveness of two non-pharmacological approaches for dementia care (*TB and PB*) in reducing the use of antipsychotic medications and behavioral and psychological symptoms in NH residents living with dementia.

Aim 2: Determine the effectiveness of the two non-pharmacological approaches on NH residents living with dementia and staff safety and wellness.

Aim 3: Identify benefits, limitations, barriers, and facilitators of each approach from the perspectives of the NH staff and NH residents' families. This qualitative data will augment the resident-level quantitative data by more fully capturing the impact of the two approaches on resident outcomes; resident-staff, staff-family, and resident-family interactions; and staff job roles before and after the emergence of COVID-19, which will guide future implementation.

Study Design & Methods

The study was initiated in January 2018. As of March 2020, 80 NHs had been recruited, randomized and staff training delivered. The COVID-19 pandemic emerged in early March 2020. Subsequent national lockdown of NHs and leadership requests to not communicate with the NHs as they navigate the early days of the pandemic resulted in a pause on all research related communication between the study team and study sites.

As the pandemic evolved, the study team developed a plan for moving forward, which included assessing the ability for NHs to re-engage in the study. Due to the negative impact of the pandemic, 27 of the 80 NHs were unable to re-engage. The remaining 53 NHs were included in the revised study protocol. This change resulted in the original cluster randomized control trial becoming two sets of exploratory analyses differentiated by the emergence of the COVID-19 pandemic.

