where $Outcome_{ijt}$ is a binary variable of having the outcome measure of interest for resident j residing in NH i at time t . $Post$ is an indicator for being in the follow-up period after implementation of approaches, which would be 1 for $t=1$ and 0 for $t=0$. TB is an indicator for NH i , which would be 1 if assigned to team-based approach arm and 0 if assigned to problem-based approach arm. The comparative effectiveness (treatment effect) of the team-based approach relative to the problem-based approach would be estimated with β_2 , which is the coefficient estimate of $post_t \times TB_i$ representing residents in team-based approach NHs during the respective follow-up period while accounting secular time trends ($post_t$) and time invariant characteristics of NH using nursing home fixed effects (NH_i). In addition, the model accounts for a set of individual resident characteristics including age, sex, race/ethnicity, Cognitive Function Scale, number of valid assessments resident had for outcome during period (X_{ij}). Models were analyzed using complete case analysis. Standard errors were clustered at the NH level. Linear probability models were implemented for ease of interpretation; regression coefficients and standard errors are presented in percentage point units. Robustness checks were conducted by implementing logistic regression difference-in-differences models with NH characteristics rather than NH-level fixed-effects to estimate the treatment effect. Marginal effects from the logistic models were computed to complement the linear probability regression models.⁴⁰ Finally, stratified analyses were conducted to examine whether treatment effects were different among residents with moderate to severe dementia vs. mild dementia. All analyses were conducted using Stata 14.0 (Stata, College Station, TX).

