For resident-level primary and secondary outcomes, we conducted difference-in-differences analyses using baseline data and the first six months of post-implementation data (six-month outcomes; September 15, 2019 to March 14, 2020) to compare outcomes across the two study arms, prior to the emergence of the pandemic. Next, we conducted analyses of resident outcomes after the emergence of pandemic spanning post-implementation months (a) 7-12 (March 15, 2020-September 14, 2020) and (b) 13-18 (September 15, 2020-March 14, 2021) (12-month and 18-month outcomes analyses, respectively). Observations with missing resident covariates were excluded from the analyses.

For staff and resident secondary safety outcomes, we calculated the monthly rate (per 100 residents) of each outcome for each NH that submitted data each month. We averaged the

monthly measures available for each NH and then examined descriptive statistics (e.g., mean) to compare the outcomes across two arms during the first five months of implementation.

Qualitative Analysis

The objectives of the staff analyses were to explore (a) perceived barriers and facilitators surrounding the intervention approach, (b) perspectives on the training modules (e.g., adequacy, acceptability, satisfaction, burden), (c) the quality of resident-staff interactions (i.e., how staff training contributed to patient outcomes) and (d) training program recommendations for modifications (i.e., sustainability, scalability). We used a three-phase team-based rapid qualitative analysis approach.^{41,42} In phase one, interview transcripts were reviewed and summarized by domains (based on interview questions) and categories (emerging inductively) into a coding template. Phase two required reviewers to reduce, synthesize, and look for similarities and differences in the data through the use of matrices. In phase three, summary tabulation procedures occurred in which reviewers combined data (e.g., NH cases, care approaches), developing themes.⁴² We explored patterns and variations in themes within and across cases and care approaches.^{43,44}

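### Should the main difference-in-differences model include a resident term linking each resident's baseline and follow-up records?

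*Combined protocol and SAP*

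**What the plan says.** The estimating equation in Statistical Considerations has a period term, a period-by-arm term whose coefficient is the treatment effect, resident covariates, home effects and an error. The home effects account for "time invariant characteristics of NH using nursing home fixed effects". The outcome is binary and defined "for resident j residing in NH i at time t", so in each comparison a resident contributes at most one baseline and one follow-up record. The covariates include age, sex, race/ethnicity, the Cognitive Function Scale and the "number of valid assessments resident had for outcome during period". On variance: "Standard errors were clustered at the NH level". The logistic robustness check swaps home effects for home characteristics and adds no resident term.

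On who is in the sample, Eligibility Criteria asks for long-stay residents aged 65 or older with dementia or cognitive impairment and sets no rule about presence at baseline. Statistical Considerations calls the analysis complete case and adds: "Observations with missing resident covariates were excluded from the analyses". Nothing states whether a follow-up window is open to newcomers.

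**The concern.** If residents leave and others arrive between windows, the plan's fit weights residents seen once and residents seen twice alike. It then makes less use of the within-resident change than it could, and differences between leavers and newcomers enter at full weight. Clustered standard errors report that loss of precision honestly but do not recover it.

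Precision is scarce here: Study Design & Methods says "27 of the 80 NHs were unable to re-engage", leaving 17 team-based and 36 problem-based homes. Turnover may also be tied to the outcomes. Scientific Background describes untreated symptoms as "increasing the risk of hospitalization and death" and off-label antipsychotics as causing harm, "including an elevated risk of death". The follow-up windows have midpoints about 9, 15 and 21 months after the baseline midpoint, so overlap with baseline probably shrinks. A resident random intercept in the same linear model looks like a cheap way to gain precision and to rely less on turnover.

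**Working it through.** **Inputs.** From the documents: 53 homes, 17 and 36 (17 + 36 = 53; 80 − 27 = 53). There is no sample size, power or effect size to reproduce. Assumed: 60 residents per home per period (the eligibility floor), prevalence 23% (the background figure for off-label antipsychotics), within-resident correlation ρ, share of residents seen in both periods λ, and home-by-period standard deviation τ. The documents give none of the last three.

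**Precision without home-by-period variation.** For the change within a home, the plan's variance is proportional to 1 − λρ, and the random-intercept variance to (1 − ρ)/(1 − ρ + λρ). Their ratio (random intercept over plan) is

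(1 − ρ) / {[1 − (1 − λ)ρ][1 − λρ]}.

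Example with λ = 0.6 and ρ = 0.6: 0.4/(0.76 × 0.64) = 0.822. The standard-error ratio is √0.822 = 0.907, worth 53/0.822 − 53 ≈ 11 homes.

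| ρ | SE ratio, λ = 0.7 | SE ratio, λ = 0.5 | Equivalent extra homes |
|---|---|---|---|
| 0.2 | 0.995 | 0.994 | under 1 |
| 0.4 | 0.973 | 0.968 | about 3 |
| 0.6 | 0.917 | 0.904 | 10–12 |
| 0.7 | 0.863 | 0.843 | 18–22 |

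At λ = 0 or λ = 1 the ratio is exactly 1. In a closed two-period sample with time-constant covariates the treatment coefficient does not change at all.

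**Precision with home-by-period variation.** The plan's variance for the treatment effect becomes

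(1/17 + 1/36) × [2p(1 − p)(1 − λρ)/60 + 2τ²],

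and the random-intercept version replaces 1 − λρ with (1 − ρ)/(1 − ρ + λρ). At ρ = 0.7 and λ = 0.5, among the most favourable cases in the table:

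| τ (points) | Plan SE | Random-intercept SE | Ratio | Equivalent extra homes |
|---|---|---|---|---|
| 0 | 1.82 | 1.54 | 0.84 | 21.6 |
| 3 | 2.21 | 1.98 | 0.90 | 13.0 |
| 5 | 2.77 | 2.59 | 0.94 | 7.6 |
| 8 | 3.80 | 3.67 | 0.97 | 3.8 |

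In simulation with unequal overlap and home size and τ = 8 points, the ratio was 1.00.

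**Validity.** In simulations with 17 and 36 homes, 60 residents each and no true effect, 95% intervals covered 90 to 95% of the time under both fits. The omission does not distort inference.

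**Turnover bias.** The result depends on what is assumed about leavers, newcomers and stayers.

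- Stayers' risk stable, turnover 50% against 30%, exit tied to the outcome and newcomers less severe: bias moved from −0.74 to −0.71, −0.60 to −0.48 and −0.58 to −0.41 points at ρ = 0.14, 0.38 and 0.57. The random intercept helps slightly.
- Selective leaving in one arm only, ρ = 0.7: −3.43 to −1.67 points. It helps clearly.
- Stayers worsening over time, home prevalence steady at 24%, turnover 50% against 30%: the plan's bias stayed within about 0.3 points, while the random intercept's ran from about 0 to −0.8. The ratio of root mean squared errors (random intercept over plan) was 0.86 to 1.03. Bias can get worse.

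**Target.** The weight on the newcomer-minus-leaver contrast is 1 − λ in the plan and (1 − λ)/[λ/(1 − ρ) + 1 − λ] with the random intercept. At λ = 0.6 and ρ = 0.7 these are 0.40 and 0.4/(0.6/0.3 + 0.4) = 0.17, so the weight on stayers' own change rises from 0.60 to 0.83. With an effect in stayers only, the estimate should therefore grow by 0.83/0.60 ≈ 1.39. Simulation at those values moved it from −4.23 to −5.83 points, a factor of 1.38. A separate simulation at ρ = 0.45 moved it from −3.67 to −4.64.

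**The case for a change.** The best argument for changing the model is that the textual facts are right and the cost is small. No term links a resident's records, the sample type is undefined, and one added term on data already extracted keeps every resident, the same scale and the same clustering. In the 34 simulated scenarios where a stayer's underlying risk does not drift, root mean squared error was lower with the random intercept every time. At high ρ the gain is worth having with 53 homes. A by-arm count of residents seen at baseline only, in both periods and at follow-up only would help any reader.

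Much of this stands. The precision gain is real if the sample is open and the outcome persists strongly within residents. The claim of less dependence on turnover does not hold in general, because those 34 scenarios leave out progression in a disease that Scientific Background calls progressive. They also set the true effect to zero, so the change of target could not appear in them. The counts would be useful in a report, but leaving them out of the plan is missing detail and does not make the analysis faulty.

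**Conclusion.** The concern does not call for a change. The model as written gives valid inference because clustering by home covers repeated records on the same resident. What remains is possible inefficiency: about 1% of the standard error at ρ = 0.2, 3% at 0.4 and 8 to 16% at 0.6 to 0.7. Those figures assume 50 to 70% overlap, an open sample and no home-by-period variation. The loss shrinks as that variation grows and vanishes in a closed sample.

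Against it, a random intercept as the main model would assume that newcomers and baseline residents of a home are alike given the covariates. It would move the target from the change in prevalence among residents present towards the change in those who stay. Both approaches train the staff of a home, and Scientific Background describes the national quality measure as a percentage of long-stay residents, so prevalence among those present is a defensible target. Reasonable statisticians could choose either fit. The analyses are labelled exploratory and are already described in the past tense, so replacing the main model now would be a post hoc choice between two defensible options. The open-or-closed question is a gap that analysts can fill with a sentence and a count table when they report.

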Exploratory quantitative analyses were conducted for 53 NHs (TB n=17, PB n=36 NHs). Primary resident-level outcomes included antipsychotic medication use, behavioral symptoms, wandering, and rejection of care, which were extracted from the Minimum Data Set and

electronic medical records. Six-month outcomes were captured prior to the emergence of COVID-19, while 12- and 18-month outcomes were after the start of the pandemic.

As a result of the COVID-19 pandemic and the significant impact it had on the study, the team bolstered the scope of the qualitative interviews from those that were originally planned. Qualitative data was collected via individual interviews with 327 NH staff (TB n=168, PB n=159) and 30 family caregivers (TB n= 13, PB n= 17) to explore their perspective of the two approaches as it relates to resident outcomes and training. Using mixed methods, quantitative and qualitative data were integrated to determine whether these sources confirm each other, provide emergent, or conflicting information.

Eligibility Criteria

Facility-level inclusion criteria required eligible NHs to (a) not have an existing dementia program targeting reduction of off-label antipsychotic medication use, (b) serve an average of >60 long-term care residents living with dementia, (c) be a CMS certified NH (e.g., conduct regularly scheduled resident assessments), and (d) comply with CMS's annual staff dementia care training requirement (i.e., 4 hours). Exclusion criteria included (a) NHs located in states that require more than four hours of dementia-specific training annually were excluded, (b) NHs that had existing dementia care programs which required staff to engage in additional training beyond the CMS minimum training requirements and more than the four hours required by the state.

Eligible NH residents included those that (a) have an existing diagnosis of ADRD or a Cognitive Function Scale score indicating Mild, Moderate, or Severe Cognitive Impairment, (b) are 65 years of age or older, and (c) are long-stay residents (>100 days). Post-acute care patients admitted for a brief stay (<100 days) and respite stay patients were excluded.

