Eligible staff were employed by a participating NH and included all staff categories, (a) professional healthcare providers, including licensed staff with professional degrees, such as registered nurses, licensed practical nurses, rehabilitation practitioners (e.g., occupational [OT], physical [PT], speech therapists [SLP]), certified therapeutic recreation specialist, dieticians, (b) direct care providers such as certified nursing assistants [CNA], activities department staff, nutrition services personnel (e.g., dining services/aids); (c) ancillary support staff, including environmental services workers (e.g., maintenance, housekeeping, kitchen staff) and administrative staff (e.g., reception, billing department, medical records); and (d) administrators, including executive directors, directors of nursing.

Eligible family caregivers were the primary contact for a resident living with dementia in a participating NH (e.g., relative, spouse, partner, friend, per neighbor).

Statistical Considerations

Descriptive analyses included calculating appropriate central tendencies (e.g., mean) for each outcome variable. We examined outcomes separately before and after the emergence of COVID-19. To assess validity of randomization, we compared resident characteristics and outcomes and NH characteristics by arm for the six-month baseline period prior to training (December 16, 2018 to June 15, 2019).

We used the intention-to-treat analytic approach to conduct the exploratory quantitative analysis. A difference-in-differences analytic model was used, rather than comparing outcomes across the arms during each six-month period after the training, to account for baseline differences in resident characteristics and outcomes. The estimating equation is as follows:

$$Outcome_{ijt} = \beta_0 + post_t\beta_1 + (post_t \times TB_i)\beta_2 + X_{ij}\delta + NH_i + u_{ijt}$$

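### The main model has no post × resident-characteristic term, so a stable difference in resident mix between arms could enter the TB-PB estimate if change over time depends on those characteristics

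*Combined protocol and SAP*

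**What the plan says.** The equation under Statistical Considerations contains post, post × TB, resident characteristics X_ij with coefficient vector δ, and home fixed effects. According to the text, "the model accounts for a set of individual resident characteristics including age, sex, race/ethnicity, Cognitive Function Scale", and also for the "number of valid assessments resident had for outcome during period". δ is the same in the baseline and follow-up windows, and no product of post and X appears. The coefficient β2 on post × TB is named as the treatment effect, described as "accounting secular time trends ($post_t$) and time invariant characteristics of NH using nursing home fixed effects".

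The section prefers difference-in-differences to comparing the arms within each follow-up window, "to account for baseline differences in resident characteristics and outcomes". It adds two supporting analyses. One is a logistic model with home characteristics in place of home fixed effects. The other is by severity: "stratified analyses were conducted to examine whether treatment effects were different among residents with moderate to severe dementia vs. mild dementia".

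The baseline window is December 16, 2018 to June 15, 2019. The six-month window ends on March 14, 2020, and the 12- and 18-month windows fall in the pandemic. Study Design & Methods reports that "27 of the 80 NHs were unable to re-engage". The analysis set is 17 TB and 36 PB homes.

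The documents do not say whether the same residents are followed across windows. They give no resident mix by arm, no change over time by resident type, and no significance level.

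**The concern.** β2 is a difference between two changes. Anything that shifts only the level of the outcome in a home is removed by the fixed effects. What can bias β2 is a difference in change that has nothing to do with the care approach. One source is resident mix: suppose one arm houses more of a type of resident whose outcome moves more over time. That arm's average then moves more, even if TB and PB work equally well in every type of resident. A single δ says that a characteristic shifts the outcome equally in both windows, so it cannot represent such a pattern.

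Two features make the question worth asking here. Baseline resident differences are the plan's own reason for choosing the model, and a third of the homes (27/80 = 34%) left after randomisation, so balance of mix cannot be taken for granted. In addition, two of the three comparisons set a pandemic period against a pre-pandemic baseline. The Scientific Background describes pandemic effects on mood, cognition and function, and the plan neither states nor tests that these were uniform across resident types.

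**Working it through.** The plan gives no figure to reproduce.

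**Algebra.** Take one binary characteristic, such as moderate-severe impairment, with share s_TB and s_PB in the two arms, stable over time. Let the outcome change by d1 in that group and d0 in the rest, with no TB-PB effect.

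- Change in TB = d0 + s_TB(d1 − d0)
- Change in PB = d0 + s_PB(d1 − d0)
- Difference = (s_TB − s_PB) × (d1 − d0)

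If the same residents are in both windows and X is fixed, X within a home is uncorrelated with post and post × TB. Adding Xδ then leaves β2 unchanged.

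**Assumed range.** The documents supply neither factor, so 5 to 15 pp is assumed for each:

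- 0.05 × 0.05 = 0.25 pp
- 0.10 × 0.10 = 1.00 pp
- 0.15 × 0.15 = 2.25 pp

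**Simulation 1: size.** From the plan: 17 and 36 homes, home fixed effects, home-clustered standard errors. Assumed: 70 residents per home per window, outcome 15% (mild) and 25% (moderate-severe), home-level SD 6 pp in baseline rate and 3 pp in change, no true effect, 2,500 runs. Monte Carlo error is about 2.32/√2500 = 0.05 pp.

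| Gap × difference in change | Formula | Mean β2, planned model | Mean β2, with post × X |
|---|---|---|---|
| 5 × 5 pp | 0.25 | 0.17 | −0.08 |
| 10 × 10 pp | 1.00 | 1.03 | 0.03 |
| 15 × 15 pp | 2.25 | 2.29 | 0.04 |

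The SD of β2 was 2.32 pp in the planned model and 2.31 pp with post × X. At 15 × 15 pp a 5% test (an assumed level) rejected in 18% of runs under the planned model and in 5% with post × X. A normal approximation shows how quickly this fades:

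- Bias 1.03 pp: 1.03/2.32 = 0.44, so rejection is Φ(−1.52) + Φ(−2.40) = 0.064 + 0.008, about 7%.
- Bias 0.25 pp: 0.25/2.32 = 0.11, so rejection is Φ(−1.85) + Φ(−2.07) = 0.032 + 0.019, about 5%.

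**Simulation 2: when the planned model works and when it does not.** Same 17 and 36 homes. Assumed: 60 residents per home per window (the threshold in Eligibility Criteria), a characteristic that raises the outcome by 15 pp, no true effect, 300 runs. Monte Carlo error is about 2.3/√300 = 0.13 pp. Entries are mean β2 in pp.

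| Scenario | No X | Planned Xδ | Xδ + post × X |
|---|---|---|---|
| Same residents, 20 pp gap, equal change in both types | 0.02 | 0.02 | 0.02 |
| Same residents, 20 pp gap, 10 pp difference in change | 2.11 | 2.11 | 0.08 |
| New residents each window, stable 20 pp gap, 10 pp difference in change | 2.06 | 2.06 | 0.03 |
| New residents, TB share moves 50% to 70%, equal change in both types | 2.95 | −0.03 | −0.03 |
| New residents, TB share moves 50% to 70%, 10 pp difference in change | 4.91 | 0.94 | −0.06 |

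With the same residents, β2 with and without X agreed to about 1e-13 pp. The planned Xδ removes a changing mix when covariate effects are constant (fourth row). It does nothing for a stable gap with a covariate-dependent change (second and third rows), and it leaves part of the bias when both operate (fifth row).

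**The case against.** Parallel trends is the ordinary assumption of difference-in-differences, and interacting covariates with time is an optional relaxation of it. The plan's rationale is a contrast with comparing the arms within each follow-up window. Difference-in-differences does remove the stable level differences at issue there. A reader might infer that the plan contradicts itself. It does not, because it never claims to adjust for covariate-dependent change.

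A reader might also infer that the resident covariates cannot adjust for mix at all. That is too strong. If residents enter and leave, which is plausible over roughly two years in long-stay residents aged 65 or older, Xδ corrects a mix that shifts differently by arm. The count of valid assessments can also vary by window, even in a fixed cohort.

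The severity fits carry weight too. If the strata are fitted separately, each has its own post coefficient, so bias arising from the mild versus moderate-severe split disappears within them. The logistic check covers a little more. A common log-odds shift of, say, 0.5 moves 15% to 22.5% and 25% to 35.5%, which allows (35.5 − 25) − (22.5 − 15) = 3 pp of differential change without any interaction.

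Finally, the analyses are declared exploratory, and most of the assumed range is small against sampling error.

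All of this stands, and it limits the point without removing it. The stratified fits are presented as a check for different treatment effects. They do not alter the main β2, and they do not address change that depends on age, sex or race/ethnicity. The logistic model has no described post × resident term.

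**Conclusion.** The main β2 is not adjusted for change over time that depends on resident characteristics. If the arms have a stable difference in mix and such change exists, β2 absorbs the product of the two. On the assumed 5 to 15 pp for each factor, that is 0.25 to 2.25 pp. It is minor at the low end and comparable with the simulated SD of about 2.3 pp only at the top. The SD itself rests on the assumed residents per home and outcome rates.

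It does not follow that the reported TB-PB effect is in fact driven by resident mix. Bias needs both factors. With a 20 pp gap and equal change in both resident types it was 0.02 pp, which is none. The documents show neither factor, and therefore no direction of bias. Nor can 17 versus 36 homes be read as unequal loss, because the original allocation is not given.

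The change is still worth making. The comparison is the study's main quantitative result, the condition is plausible in the two pandemic windows, and the covariates are already held.

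**What to change.** For each window, fit the current model with added terms post × (age, sex, race/ethnicity, Cognitive Function Scale), each characteristic centred at its overall mean. Keep β2 on post × TB as the TB-PB effect, and report it beside the current common-δ estimate. If the two differ, temper the TB-PB conclusion for that outcome and window.

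Use the pre-training Cognitive Function Scale where available, since a later value could itself respond to the care approach. The number of valid assessments can keep its single coefficient, because it describes follow-up in the window more than the type of resident. State whether residents form a fixed cohort or are re-sampled in each window, and give the baseline mix by arm from the comparison already planned. The reader can then judge the size of the gap.

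The cost is a few extra terms and one more reported estimate per outcome and window. Precision was essentially unchanged in the simulations (SD 2.32 versus 2.31 pp). Centring keeps β1 readable as the change in PB homes at the average resident mix.

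### Standard errors clustered on 17 versus 36 homes with no stated small-sample correction: intervals for beta_2 probably about 3 to 8% too narrow, and a nominal 5% test rejects at about 6 to 7%

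*Combined protocol and SAP*

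**What the plan says.** Statistical Considerations gives a difference-in-differences equation with home fixed effects. Beta_2, on the product of the follow-up and team-based indicators, is the treatment effect. On inference it says "Standard errors were clustered at the NH level", and on presentation "Linear probability models were implemented for ease of interpretation; regression coefficients and standard errors are presented in percentage point units". The software statement is "All analyses were conducted using Stata 14.0". No cluster-variance variant, critical value, degrees of freedom, bootstrap or randomisation test is mentioned, and no alpha level is given.

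Study Design & Methods supplies the number of clusters: "Exploratory quantitative analyses were conducted for 53 NHs (TB n=17, PB n=36 NHs". These homes are what remained of the 80 randomised, because "27 of the 80 NHs were unable to re-engage". The same section describes what is left as exploratory.

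The sensitivity analysis is described as follows: "Robustness checks were conducted by implementing logistic regression difference-in-differences models with NH characteristics rather than NH-level fixed-effects". It changes the link function and the adjustment for homes. It does not address how the variance behaves with few, unevenly split clusters.

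The home-size distribution is not given. Eligibility Criteria sets only a floor, an average of more than 60 long-term care residents with dementia per home.

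**The concern.** Once home effects are absorbed, beta_2 is a size-weighted difference between the mean change in 17 homes and the mean change in 36. The usual cluster-robust variance is a large-sample formula. With few clusters in one arm it is biased downward, because each home pulls its own arm mean towards itself. The usual G-1 = 52 degrees of freedom also overstate how well that variance is estimated, since most of the uncertainty comes from the 17 homes. Unequal home sizes make both effects worse.

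Both errors act in the same direction: standard errors too small and critical values too low. The study question in Study Objectives is framed in terms of statistical significance. The same recipe serves all resident-level outcomes, the three follow-up windows and the severity strata, so the error repeats.

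**Working it through.** The plan gives no standard error, interval, alpha or intracluster correlation, so there is no figure of its own to reproduce.

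**Inputs from the document:** 17 and 36 homes (G = 53), home fixed effects, clustering by home, Stata 14.0, and the floor of more than 60 residents.

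**Assumptions:** two-sided 5% test; default cluster variance (CR1), meaning a factor G/(G-1) = 53/52 and t on 52 degrees of freedom; z for a logistic model; outcome prevalence 20%; home-size coefficient of variation (CV) from 0 to about 1.

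**Step 1: the 17/36 split alone (equal sizes, equal variances).**

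- True variance is proportional to 1/17 + 1/36 = 0.08660.
- Expected default variance: [(16/17)/17 + (35/36)/36] × 53/52 = 0.08237 × 1.0192 = 0.08395.
- Ratio 0.08395/0.08660 = 0.969, so the standard error is √0.969 = 0.985 of the truth (root expected variance; the simulated mean standard error is about 0.975).
- Satterthwaite degrees of freedom: 0.08660² / [(1/17)²/16 + (1/36)²/35] = 0.007500/0.0002383 = 31.5, not 52.
- Critical values: t(52) = 2.007, t(31.5) = 2.038, z = 1.960.
- Interval width relative to the corrected one: 0.985 × 2.007/2.038 = 0.969, so 3.1% too narrow. With z: 0.985 × 1.960/2.038 = 0.947, so 5.3% too narrow.

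For comparison, a balanced 26/27 split at equal sizes rejects at 5.2% with t(52). The imbalance, more than the total of 53, drives the problem.

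**Step 2: unequal sizes, simulated under no effect.** Resident-level binary data, 20,000 replicates per scenario, equal arm variances. Each range covers three levels of between-home variation in change. Narrowing is 1 − 2.007/q, where q is the simulated 95th percentile of |t|.

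| Size CV | Too narrow, t(52) | Rejection, t(52) | Rejection, z | Satterthwaite df | Rejection, CR2 with Satterthwaite df |
|---|---|---|---|---|---|
| 0 | 3.3–4.1% | 5.7–5.9% | 6.2–6.5% | 31.5 | 5.1–5.3% |
| 0.31 (floor 60, mean 90) | 2.9–3.9% | 5.7–5.8% | 6.3–6.4% | 29 | 4.8–5.0% |
| 0.49 | 3.9–6.2% | 6.0–6.5% | 6.5–7.1% | 25.5 | 4.9–5.3% |
| 0.68 | 4.5–7.9% | 6.0–6.9% | 6.6–7.6% | 22 | 4.7–5.3% |
| 0.93 | 6.7–12.7% | 6.7–8.4% | 7.2–9.2% | 18 | 4.8–5.8% |

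The closed form behind these runs matched a resident-level clustered regression (0.01686 both ways).

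**Step 3: unequal arm variances.** If changes in team-based homes have 1.5 to 2 times the SD of those in problem-based homes, rejection with t(52) is about 7% at CV 0.5, about 7.5% at CV 0.7, and 8.8% (9.5% with z) at CV near 1. At CV 0.7, reaching about 9% takes a doubled team-based SD and z critical values.

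If problem-based homes vary more, the excess shrinks. With equal sizes and team-based SD half the problem-based SD, the variance ratio is [0.25 × (16/17)/17 + (35/36)/36] × (53/52) / (0.25/17 + 1/36) = 0.0416/0.0425 = 0.980. The standard error is then about 1% low. Simulated rejection in this direction, at SD ratios of 0.5 to 0.67, stays between 5 and 6% for equal sizes and for sizes with the floor.

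**The case against.** A reader might infer that intervals are generally 10% too narrow and that the test runs at 9%. The documents do not support this. With a mean of 90 and a floor of 60, the excess over the floor averages 30. An exponential excess gives a CV of 30/90 = 0.33, and a CV of 1 would need that excess to have an SD of 90. Without a floor, a lognormal with mean 90 puts 37% of homes below 60 residents at CV 0.7 and 47% at CV 1. The two figures are also not one scenario: 10% narrowing alone gives about 7.8% rejection, and 9% needs about 13.5%. Nothing in the documents suggests that team-based homes vary more.

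A reader might also infer that every published interval and p-value is wrong. The document says only that coefficients and standard errors are presented, and it does not name the variance variant. A correction may have been applied without being described.

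Finally, clustering at the randomised unit with 53 clusters is accepted practice, the analysis is labelled exploratory, and one percentage point of extra rejection is small beside the loss of 27 of 80 homes.

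All of this limits the size of the point, and it stands. It does not reverse the direction: step 1 uses only the stated 17/36 split and the assumed default estimator. The exploratory label does not make a nominal 95% interval correct. The floor also gives less reassurance in the severity strata, because it applies to the whole home and not to the subgroup counts.

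**Conclusion.** The point holds as a modest calibration issue. If the default cluster variance was used with a two-sided 5% test, intervals for beta_2 are about 3% too narrow and rejection is just under 6% with equal home sizes. Rejection is about 6% with sizes that respect the eligibility floor. For assumed size CVs of 0.5 to 0.7 with equal arm variances, intervals are about 4 to 8% too narrow and rejection is about 6 to 7%. Around 9%, or slightly more in the worst corner, needs a size CV near 1, or strongly unequal arm variances together with z critical values. Such conditions are more plausible in the severity strata than in the full sample.

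Home sizes, arm variances, prevalence, alpha and the variance variant are all assumptions; only the 17/36 split, the clustering and the software are stated. The change is worth making but not essential.

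**What to change.** Keep the model, the estimand and clustering by home. For every beta_2, including the severity strata, report bias-reduced (CR2) standard errors with Satterthwaite degrees of freedom, or restricted wild cluster bootstrap intervals and p-values. In the simulations, CR2 with Satterthwaite degrees of freedom brought rejection to 4.7 to 5.3% for size CVs up to 0.7, and 4.8 to 5.8% near 1.

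State the variance variant and degrees of freedom used, say whether the logistic check uses t or z, and report the distribution of home sizes by arm so that readers can judge the size of the effect.

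The cost is a sentence in the analysis plan, a rerun on existing data, and intervals wider by about 3 to 8%: 1/0.969 = 1.03 at equal sizes, about 1/0.940 = 1.06 at CV 0.7, and 1/0.927 = 1.08 or a little more at CV near 1.
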